13.8.4 Follow-up Procedures

There are no specific follow-up procedures for subjects once they have been discharged or completed the 28-day trial period. Trauma Research Fellows will collect study information including AEs and SAEs by as per the Schedule of Assessment (Section 13.8.2).

In order to ensure completion of follow-up for SAEs for subjects who are discharged from hospital prior to 28 days, an investigator will attempt to contact the subject or their General Practitioner by telephone on or around 28 days to encourage reporting of any SAEs occurring following discharge. Subjects will be provided with details of whom to contact if they have any questions regarding the trial or wish to provide further information.

Study patient 90-day mortality follow-up shall be conducted using data obtained via the NHS spine services (Health and Social Care Information Centre). It is not practicable to attempt to approach subjects to request "their" survival data; such actions are precluded because there is sufficient potential to do harm and cause distress by inadvertently approaching the families of deceased study subjects.

13.9 Withdrawal criteria

Every reasonable effort will be made to maintain protocol compliance and to retain patient participation in the study consistent with the provisions of informed consent and good clinical practice. The following are potential reasons why a patient may be withdrawn from the study:

- 1. Withdrawal of consent: the patient, the patient's authorised representative, independent physician, or designated individual who had provided initial consent to enter the study may withdraw consent at any time throughout the duration of the trial, without prejudice to future medical care and treatment.
- 2. Retrospective exclusion: If a patient is deemed to not meet one or more of the inclusion/exclusion criteria in retrospect they will be withdrawn from the study.
- 3. Major protocol deviation from the study design by the subject, observed or suspected by the investigator.
- 4. Adverse event.
- 5. Administrative: the sponsor or monitoring committees decide to terminate or discontinue the study.
- 6. The subject's health would be jeopardised by continued participation and is withdrawn at the discretion of the investigator.

Data Collection And Follow-Up For Withdrawn Subjects

If a patient is withdrawn from the study before receiving IMP but after randomisation, any ongoing SAE experienced by the patient, which are not injury- or standard-treatment related, will be followed to resolution but no other safety or efficacy assessments will be conducted.

Patients who withdraw from the study after receiving IMP should be followed for safety by conducting safety assessments through to the end of day 28. If a patient who withdraws has develops an SAE during the monitoring period, every effort must be made to follow such events until satisfactory resolution is obtained or until further follow-up is no longer warranted.

Any samples obtained from withdrawn participants will be discarded in accordance with the Bart's Health NHS Trust standard procedures.

Replacement Of Subjects

Subjects who do not complete the primary outcome end-point at 48-hours (e.g. due to death or discharge) will be replaced. Subjects who withdraw from the study at any time point will also be replaced. Withdrawn participants will not be permitted to re-enter the study.

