13.3.2 Consent Considerations

The right of a participant to refuse participation without giving reasons will be respected.

The participant must remain free to withdraw at any time from the trial without giving reasons and without prejudicing his/her further treatment and must be provided with a contact point where he/she may obtain further information about the trial. Where a participant is required to re-consent, for example if during the trial new Research Safety Information becomes available, or following an

amendment that affects the patient, or new information needs to be provided to a participant, it is the responsibility of the PI to ensure this is done in a timely manner.

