19.0 Statistical and Data Analysis

19.1 Sample size calculation

The primary objective of this trial is to determine the signs of potential efficacy of Artesunate in reducing multiple organ failures and complications. To establish this, the primary comparison of interest will be on the SOFA score at 48 hours.

Each of the Artesunate dose level groups will be compared to placebo. For each dose level the null hypothesis will be that there is no difference in the response rates between Artesunate and placebo, the alternative hypothesis being that the response rate is higher for Artesunate than for placebo.

This is a Phase 2a study and we are looking for safety and efficacy data with which to appropriately power a subsequent definitive 2b trial. A formal sample size calculation is not possible given the lack of existing human efficacy data.

However if Artesunate leads to a clinically relevant 2-point reduction in 48-hour SOFA score, this study will have a power of 80% to detect this difference with 70 intervention and 35 control subjects (α =0.05; σ =3.43) by unpaired t-test.

The intervention arms will consist of 35 subjects receiving Artesunate at 2.4 mg/kg and 35 receiving Artesunate at 4.8 mg/kg. We shall also perform two one-sided t-tests on each of the two intervention arm does levels against the placebo where 35 patients in each arm will detect a 2-point reduction in 48-hour SOFA (α =0.05; σ =3.43) with 78% power.

This should provide enough data on safety profile and potential clinical efficacy to determine whether progression to a 2b study is justified and to develop an appropriate study protocol.

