19.10 Subject population

The analysis populations will be defined as follows:

Intent-to-Treat (ITT) Population

The ITT population is defined as all patients randomised according to their treatment allocation irrespective of whether they received that treatment or not.

Per Protocol (PP) Population

Version 2.0 TOP-ART

The PP population is defined as all patients randomised and treated according to the protocol i.e. based on treatment that patients actually received. The primary efficacy analysis will be performed on this study population.

Safety Population

The safety population is defined as all patients randomised who received any partial dose of IMP and will be analysed based on treatment that patients actually received.

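### Section 13.9 bars or does not assure efficacy follow-up for randomised patients withdrawn for reasons other than consent, although the ITT set includes them

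*Protocol*

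**What the plan says.** Protocol section 13.9 lists six possible reasons for withdrawal from the study: (1) withdrawn consent, (2) ineligibility found in retrospect, (3) a major deviation by the subject, seen or suspected by the investigator, (4) an adverse event, (5) termination by the sponsor or committees, and (6) jeopardised health, at the investigator's discretion. Two data rules follow, split at dosing.

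- **Randomised but not yet dosed:** ongoing serious adverse events that are not due to the injury or standard treatment "will be followed to resolution but no other safety or efficacy assessments will be conducted".
- **Dosed:** "Patients who withdraw from the study after receiving IMP should be followed for safety by conducting safety assessments through to the end of day 28". Efficacy is not mentioned.

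All withdrawn patients are replaced. Section 19.10 defines the ITT population as "all patients randomised according to their treatment allocation irrespective of whether they received that treatment or not". Section 19.5 commits to both ITT and per-protocol analyses and makes the per-protocol analysis the main one. Section 19.11 provides for imputing missing outcomes where appropriate. Under section 15.13 treatment is one intravenous bolus given over 1-2 minutes. On consent, section 13.3.2 states: "The participant must remain free to withdraw at any time from the trial without giving reasons".

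**The concern.** The protocol plans an analysis of all randomised patients and, in another section, stops sites from collecting the outcomes that analysis needs. A statistical analysis plan can choose how to handle missing values, but it cannot recover data that sites were told not to collect.

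Only reason 1 expresses a patient's wish that collection should stop. Reasons 2, 3, 4 and 6 are judgements made after randomisation. Once a patient is dosed there is no treatment left to stop, so withdrawal from the study can change only what is recorded afterwards. Before dosing, the person preparing the injection knows the allocation (sections 13.5.2 and 13.6), so a withdrawal at that point could depend on the arm. The ITT analysis is the one planned comparison that keeps the randomised groups intact. It is weakened if its missing members are those who were sicker, or whose allocation was known when they were removed.

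**Working it through.** **1. The sections side by side**

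- *Withdrawn before dosing, reasons 2, 3 or 6.* In the ITT set under 19.10; efficacy assessment barred by 13.9. This is a direct conflict.
- *Withdrawn after dosing, reasons 2, 3, 4 or 6.* In the ITT set; 13.9 requires safety assessments to day 28 and neither requires nor forbids efficacy assessments. The safety bloods in 13.8.3 are daily on days 1-7 for patients still in hospital, and supply platelets, bilirubin and creatinine. Those are three of the six SOFA components in Appendix 2. The respiratory, cardiovascular and GCS components are not covered, so a full 48-hour SOFA is not assured.
- *Mortality.* Death meets the definition of a serious adverse event (17.1), so safety follow-up would show deaths to day 28 in dosed patients. Status at 90 days comes from NHS Spine without patient contact (13.8.4).

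**2. The plan's own figures**

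Section 19.1 says "the primary comparison of interest will be on the SOFA score at 48 hours". The inputs are a 2-point difference, SD 3.43, alpha 0.05 and the unpaired t-test.

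- 70 v 35: noncentrality 2 / (3.43 × √(1/70 + 1/35)) = 2.82; two-sided power 79.7% (stated 80%).
- 35 v 35: noncentrality 2 / (3.43 × √(2/35)) = 2.44; one-sided power 77.9% (stated 78%).

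Both reproduce. Nothing in this point changes the stated power.

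**3. Replacement restores the count, not the outcomes**

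The protocol gives no withdrawal rate, so the rates here are assumed. The number randomised to reach 105 evaluable patients is 105/(1 − w), rounded up:

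- w = 2%: 108
- w = 5%: 111
- w = 10%: 117
- w = 20%: 132

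That leaves 3, 6, 12 or 27 ITT members who may have no recorded 48-hour SOFA.

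**4. Possible shift in one arm's mean (assumed inputs)**

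Suppose 35 + k patients are randomised to an arm and k are lost and replaced. If each lost patient lies d points above the full arm mean, the mean of the 35 retained is too low by k × d / 35.

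- k = 1, d = 6: 6/35 = 0.17 points, or 9% of the 2-point target.
- k = 3, d = 8: 24/35 = 0.69 points, or 34%.

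**5. Effect on a complete-case comparison with no true effect (assumed inputs)**

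Bias = (withdrawal rate in active − rate in placebo) × D, where D is the SOFA gap between withdrawn and retained patients. Take 10% v 0%, with 70 v 35 retained:

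- D = 2: bias 0.2; two-sided error rate about 5.9%.
- D = 4: bias 0.4; about 8.6%.
- D = 6: bias 0.6; about 13.3%.

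Equal withdrawal rates with the same D in both arms would give no bias in the difference.

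**The case against.** The strongest reply is that the explicit bar covers a narrow window. Preparation takes about six minutes, and dosing is due within two hours of admission. The adverse event definition in 17.1 presupposes that the product has been given, so reason 4 hardly arises before dosing. Reason 3 concerns conduct by the subject, and most subjects are incapacitated. No section gives the unblinded administrator the decision to withdraw, so arm-dependent withdrawal is possible but not shown. All of this stands. It limits the likely number of patients but does not remove the conflict between 13.9 and 19.10.

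A reader might go further in four ways that the documents do not support.

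- *That the ITT analysis cannot be run.* Section 19.11 allows imputation. What is lost is an ITT analysis on observed outcomes.
- *That all outcome data stop, including 28-day deaths.* After dosing the protocol is silent on efficacy rather than prohibitive. Some SOFA inputs continue, and deaths to day 28 would be seen.
- *That the primary result is distorted.* Undosed and ineligible patients fall outside the evaluable set in 19.12 in any case. For dosed patients the text does not say that the 48-hour SOFA is omitted, so no loss is established.
- *That safety follow-up overrides withdrawn consent.* Section 13.9 opens by tying retention to the consent provisions, 13.3.6 says a refusal to continue will be respected, and 13.8.3 lets the subject decline research bloods. The follow-up sentence just does not repeat this.

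**Conclusion.** The point holds in a limited form. For patients withdrawn before dosing, 13.9 contradicts the ITT population in 19.10 and the analysis required by 19.5. For patients withdrawn after dosing, it fails to assure the 48-hour SOFA and later efficacy outcomes. The ITT analysis would then depend on imputing values that could have been observed.

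The size is unknown. The only withdrawal figure in the protocol is one consent withdrawal in an earlier trial at the centre (19.2), which says nothing about withdrawals decided by investigators. The 0.17 to 0.69 point illustration assumes losses in one arm only, of patients about 1.7 to 2.3 SDs above the mean (6/3.43 and 8/3.43). It shows what a few informative losses could do to a complete-case ITT comparison; it is not an estimate. The effect shown is on the ITT analysis and not on the main per-protocol one. The conflict should still be resolved, because it removes data at source and is cheap to correct.

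**What to change.** In section 13.9, separate withdrawal of consent to data collection from every other reason.

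- **Reasons 2, 3, 4 and 6, before or after dosing:** continue to collect the 48-hour SOFA, the other endpoints and 28-day and 90-day mortality from routine records and NHS Spine. Delete the clause that bars efficacy assessments.
- **Withdrawal of consent:** record which elements are refused (research bloods, contact, use of records, NHS Spine). Keep data already collected as permitted and stop the refused elements. State that safety follow-up to day 28 applies only where still permitted.
- **Reason 5** ends the study as a whole and needs no rule for individual patients.

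The cost is wording in the protocol, CRF and consent form, plus some extra chart abstraction for a few patients. The same sources are already used for every other participant.

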13.8.3 Trial assessments

Medical History

The medical and trauma history will be conducted at screening and should include (but not be limited to) demographic information, subjects' medical history with an emphasis on the trauma, current medication, past medication and allergies. This will be ascertained as part of the subjects' initial clinical assessment by the trauma team, and the Trauma Research Fellow. The known medical history must be documented in the subject's notes (the on-site source document) prior to IMP administration and also recorded in the CRF. Any further medical history ascertained subsequent to the initial assessment will be derived from the subjects' notes during the assessment phase.

Vital signs

Vital signs will be recorded at baseline and at PK/PD sampling points. They will also be monitored for 28 days as part of the SAE assessment process.

Systolic and diastolic blood pressures will be recorded using a standard sphygmomanometer reading or by invasive arterial monitoring (where this has been inserted as part of routine clinical care). Pulse rate and oxygen saturations will be measured by pulse oximetry or by arterial monitoring as above. Respiration rate will be assessed by observation as breaths per minute; and a tympanic body temperature measure will be used, unless other methods (e.g rectal monitoring) are in place for continuous clinical monitoring. GCS will be recorded from the subject notes or assessed clinically.

Pregnancy test

Prior to administration of any IMP a pregnancy test will be undertaken on all women of childbearing potential.

Note: The subject must not be dosed if any tests are positive.

Body weight

Body weight will be estimated to the nearest 10kg.

PK/PD Blood samples

Subjects will have 10mls of blood drawn to determine the plasma levels of Artesunate and its metabolite DHA (PK-PD study in man) at the following time points:

- At hour 0 (within 10 minutes) immediately prior to IMP dosing
- 5 (±1 minute) minutes after the start of IMP infusion
- 30 (±2 minutes) minutes after the start of IMP infusion
- 1 (±5 minutes) hours after the start of IMP infusion
- 4 (±20 minutes) hours after the start of IMP infusion
- 12 (±30 minutes) hours after the start of IMP infusion

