14.5.1 The arrangements for sample analysis

Samples for analytic studies of PK/PD analysis will be shipped to the Mahidol Oxford Tropical Medicine Research Unit, Bangkok, either as a single shipment at the end of the study, or with an additional half-way batch (approx. n=50) during the recruitment phase of the project, as agreed with the sub-contractor. The storage conditions and shipment of the samples will be conducted according the specialist laboratory instructions (see Appendix 1)

Samples will be shipped in a clearly labelled primary container and placed in a leak proof secondary container. Samples will be frozen in an upright position and the labelling of boxes and each sample will be clear and freeze resistant. Qualified couriers will be used for transportation of samples to the Mahidol Oxford Tropical Medicine Research Unit with ensured cold chain control. The research team will be responsible for arranging couriers. Please see Appendix 1 for a summary of the sample analysis and shipping arrangements as provided by the laboratory.

The Mahidol Oxford Tropical Medicine Research Unit does not supply sample collection kits for PK/PD analysis to the recruitment site. The study site will procure all sample collection tubes.

Ancillary studies related to the trial may involve the analysis of participant DNA (See Section 14.3 and 13.3.9), provided the subject has given informed consent. Information regarding samples taken for genetic research will be disseminated in the participant information sheet.

Samples taken for PK/PD analyses will initially be processed on the recruitment site to extract plasma (see Section 14.3), and shipped samples will consist of small volumes (less than 1 ml per sample), so we do not envisage any remaining sample following analysis. However, in the event there is sample remaining following analysis, these will be discarded in accordance with the HTA Code of Practice.

Samples used for ancillary studies will be stored at The Blizard Intitute, Queen Mary University of London, in accordance with HTA regulations.

We do not anticipate that the research would produce findings of clinical significance for individual donors or their relatives.

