14.5.2 Sample Storage Procedures

Samples will be stored at the Trauma Research Laboratory, Ward 12D, Barts Health NHS Trust and The Blizard Institute, Queen Mary University London prior to transfer to and analysis by the Mahidol Oxford Tropical Medicine Research Unit, Bangkok. Samples will be placed under storage conditions immediately after processing in catalogued cryoboxes.

Samples for PK/PD analysis can be stored for the duration of the study period until analysis either at the end of the study or at the halfway point, as per the specialist laboratory instructions. Serum and PAXgene samples collected for ethically approved future research studies can be stored long-term and will be stored in an ethically approved tissue bank at the Blizard Institute, Queen Mary, University of London in accordance with the Human Tissue Act.

If a participant withdraws consent, the Tissue Custodian, who is the CI, will be informed and give approval to the lab to discard any samples in accordance with the Human Tissue Act and Barts Health NHS Trust policy. This will be documented and accounted for in the accountability/sample destruction log.

Samples will be stored in specialist freezers at $-80^{\circ}C \pm 10^{\circ}C$. They will be stored in linkedanonymised form using the unique study ID. Only the research team will be able to link stored samples to personal identifiable information. The central analytical laboratory in Mahidol Oxford Tropical Medicine Research Unit, Bangkok, in addition to any collaborators involved with future ethically approved research will only have access to the de-identified samples coded by the unique study ID.

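### Section 13.9 discards samples from every withdrawn participant whatever the reason, which is wider than Section 14.5.2 and lets drug-level data go missing in a way related to toxicity

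*Protocol*

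**What the plan says.** Section 13.9 gives six potential reasons for withdrawal: withdrawn consent, ineligibility found in retrospect, a major protocol deviation by the subject, an adverse event ("4. Adverse event"), an administrative reason ("5. Administrative: the sponsor or monitoring committees decide to terminate or discontinue the study"), and the investigator's judgement that continuing would jeopardise health.

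The part of the same section on withdrawn subjects makes two provisions that matter here. On follow-up: "Patients who withdraw from the study after receiving IMP should be followed for safety by conducting safety assessments" up to the end of day 28. On samples: "Any samples obtained from withdrawn participants will be discarded in accordance with the" Trust's standard procedures. The second provision is not limited by reason for withdrawal, by whether the drug was given, or by type of sample.

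Section 14.5.2 addresses one of the six cases: "If a participant withdraws consent, the Tissue Custodian, who is the CI, will be informed and give approval to the lab to discard any samples", with the disposal documented in a log.

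The samples at stake are described in Section 13.8.3: "Subjects will have 10mls of blood drawn to determine the plasma levels of Artesunate and its metabolite DHA (PK-PD study in man"), at six time points from just before dosing to 12 hours. Under Section 14.5.1 they are shipped for assay "either as a single shipment at the end of the study, or with an additional half-way batch (approx. n=50) during the recruitment phase". Section 19.10 puts everyone who received any part of a dose in the safety population.

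**The concern.** A discard rule tied to withdrawn consent protects the participant's wishes. A rule tied to any withdrawal goes further: it also destroys samples from people who never objected to their use. When the reason for withdrawal is an adverse event or the investigator's concern for the patient's health, the missing drug levels are linked to possible toxicity. The patient's adverse events are still counted to day 28, but the exposure that went with them can no longer be measured.

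These samples are the only direct measure of exposure in the trial. Body weight is estimated to the nearest 10 kg (Sections 13.8.3 and 15.10), so the nominal dose per kilogram is approximate. Two things would be at stake: the drug-level summary for each dose group, and any later look at exposure against adverse events. Once samples are destroyed, no analysis plan can recover them.

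**Working it through.** **Step 1: scope of the two rules.**

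| Reason for withdrawal (13.9) | Discard under 13.9 | Discard described in 14.5.2 |
|---|---|---|
| 1. Consent withdrawn | Yes | Yes |
| 2. Ineligible in retrospect | Yes | Not addressed |
| 3. Major deviation by the subject | Yes | Not addressed |
| 4. Adverse event | Yes | Not addressed |
| 5. Administrative or study stopped | Yes | Not addressed |
| 6. Health jeopardised, investigator's discretion | Yes | Not addressed |

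The sections agree on one row of six. Read literally, row 5 would also discard samples if the study were stopped early.

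**Step 2: would the samples still be unassayed?** Sampling ends at 12 hours. A subject is in the study for 28 days or until discharge (Section 11.6). Shipment is at study end, or with one optional batch at about half-way. A withdrawal within 28 days will therefore nearly always come before the assay. Levels already measured in a half-way batch would survive.

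**Step 3: what survives.** Adverse events are followed to day 28 after post-dose withdrawal, and clinical and safety blood results are recorded as data. The loss falls on stored research samples.

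**Step 4: amount of data.** Active-arm subjects: 35 + 35 = 70. Samples: 6 × 70 = 420. The protocol states no withdrawal rate, so I assume two values. The first, 1.5%, borrows the ceiling that Section 9.2 puts on each listed drug risk; it is not a withdrawal rate. The second, 10%, is a high value chosen for illustration.
- 1.5%: 0.015 × 70 = 1.05, about 1 profile (6 samples).
- 10%: 0.10 × 70 = 7 profiles (42 samples).

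**Step 5: possible bias in mean exposure.** If withdrawal is unrelated to exposure, the bias is zero. As an upper bound for a given withdrawal rate p, assume lognormal exposure with CV 50% and that exactly the highest fraction p is withdrawn.

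s² = ln(1 + 0.5²) = 0.2231, so s = 0.472.
Ratio of observed mean to true mean = Φ(z − s)/(1 − p), where z is the (1 − p) standard normal quantile.

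- p = 1.5%: z = 2.170, z − s = 1.698, Φ = 0.9552; 0.9552/0.985 = 0.970, or 3% low.
- p = 5%: z = 1.645, z − s = 1.172, ratio 0.926, or 7% low.
- p = 10%: z = 1.282, z − s = 0.809, Φ = 0.791; 0.791/0.90 = 0.879, or 12% low.

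The CV, the values of p and the perfect selection are all assumptions. The protocol has no figure of its own to reproduce here.

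**The case against.** Several counter-arguments carry weight.

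- **The sections are compatible.** Section 14.5.2 says what happens when consent is withdrawn; it does not say that this is the sole trigger. A laboratory could follow both. This stands: it is a mismatch of scope, not a strict contradiction. It does not remove the effect of the wider rule in 13.9.
- **Drug levels are not an endpoint.** They appear in none of the endpoint lists, Section 11.4 gives no exploratory endpoints, and the protocol prescribes no exposure-safety analysis. This stands and limits the importance of the point. The protocol nevertheless takes six samples per patient for this purpose.
- **Withdrawal for an adverse event may be rare.** The list is of potential reasons. The drug is a single bolus, a reaction during dosing leads to stopping the injection (Section 15.15), and death is not a listed reason. The frequency is indeed unknown, but Section 19.9 plans to tabulate adverse events leading to withdrawal, so the protocol expects that some may occur.
- **Selection on exposure is speculative.** Section 9.1 reports no dose-related rise in adverse events up to 8 mg/kg in volunteers, apart from a fall in reticulocytes, and many events here will come from the injury. This is why the bias figures are bounds and not estimates.

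A reader might infer two stronger points that the documents do not support. One is that samples would be lost after a dosing or preparation error. Reason 3 covers deviations by the subject, whereas trial staff prepare and give the drug, and Sections 15.12 and 15.15 have dose changes recorded without making them grounds for withdrawal. The other is that the loss bears on the decision to go to the higher dose. Section 19.9 bases that decision on adverse events, vital signs and laboratory values, and nothing feeds drug levels into it.

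**Conclusion.** The point holds as a limited one. Section 13.9 goes beyond Section 14.5.2 and, as written, destroys unassayed drug-level samples from dosed participants withdrawn for an adverse event, retrospective ineligibility, investigator discretion or an administrative reason, although those participants stay in the safety population and in follow-up to day 28. Missing drug-level data can then be related to toxicity.

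The primary SOFA comparison, the listed secondary and safety endpoints and the interim decision are unaffected. The size is unknown: it runs from lost data with no bias to a mean exposure about 3% low (1.5% withdrawn) or 12% low (10% withdrawn) under assumed perfect selection at CV 50%. It would be wrong to read those figures as an expected bias, since the protocol supports neither the rates nor the selection. The case for the change is that the loss is irreversible and avoiding it costs very little.

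**What to change.** Reword the sample sentence in Section 13.9 so that samples are discarded only when the participant or legal representative withdraws consent and does not agree to retention. Add that samples from dosed participants withdrawn for any other reason are kept, assayed and included in the drug-level summaries. Make Section 14.5.2 refer to the same rule.

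The cost is a sentence or two in the protocol and a check that the information sheet and consent form match. No further samples or patients are needed, and a participant who withdraws consent can still have the samples destroyed.
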